An early placebo-controlled study showed that nabilone, a synthetic THC, dramatically reduced anxiety in anxious patients⁹⁶. These anxiolytic effects of eCB enhancers have sparked interest in CB1 receptors as a pharmacological target for treating anxiety disorders⁹⁷⁻¹⁰⁰. Given that extinction retention deficits and vmPFC-HPC dysfunction have been observed in patients with PTSD, and that enhancing cannabinoid transmission helps extinction recall, the cannabinoid system is a promising target for improving the learning that goes on in therapy and perhaps increasing the efficacy and durability of PE in treating PTSD (e.g., shortening treatment while strengthening and prolonging gains). However, direct tests of cannabinoid effects on extinction recall and associated neural circuits have not yet been conducted in PTSD patients. Therefore, the primary goal of the proposed project is to test the hypotheses that administration of an exogenous CB1 agonist will 'rescue' deficits in fear extinction recall in PTSD patients and that these effects will be mediated by increased activation and functional connectivity of vmPFC and HPC.

To address the issues mentioned above we propose the following specific aims:

Specific Aim 1: To assess the effects of THC on extinction memory recall and vmPFC and HPC activation and connectivity in controls (healthy controls, HC; trauma-exposed non-PTSD controls, TEC).

Hypothesis 1A: Relative to PBO, THC will decrease SCRs and US expectancy ratings to a CS that was previously extinguished (CS+E) during an extinction recall test in controls. Hypothesis 1B: Relative to PBO, THC will enhance regional activation in the vmPFC and HPC to the CS+E during an extinction recall test in controls.

Hypothesis 1C: Relative to PBO, THC will increase functional coupling between the vmPFC and HPC to the CS+E during an extinction recall test in controls.

Specific Aim 2: To compare extinction memory recall success and vmPFC and HPC activation and connectivity between PTSD patients and controls (HC/TEC).

Hypothesis 2A: Relative to controls, PTSD patients will show increased SCRs and US expectancy ratings to the CS+E during an extinction recall test.

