Hypothesis 2B: Relative to controls, PTSD patients will show attenuated regional activation in the vmPFC and HPC to the CS+E during an extinction recall test. Hypothesis 2C: Relative to controls, PTSD patients will show less functional coupling between the vmPFC and HPC to the CS+E during an extinction recall test.

Specific Aim 3: To investigate whether THC can correct extinction memory recall impairments and aberrant vmPFC and HPC activation and connectivity in PTSD patients.

Hypothesis 3A: Relative to PBO, THC will decrease SCRs and US expectancy ratings to the CS+E during an extinction recall test in PTSD patients, similar to levels observed in controls (HC/TEC). Hypothesis 3B: Relative to PBO, THC will enhance regional activation in the vmPFC and HPC to the CS+E during an extinction recall test in PTSD patients, similar to controls (HC/TEC). Hypothesis 3C: Relative to PBO, THC will increase functional coupling between the vmPFC and HPC to the CS+E during an extinction recall test in PTSD patients, similar to extent of connectivity observed in controls (HC/TEC).

B. Preliminary Data

The preliminary data here: 1) establish the capacity of the PI to carry out fMRI studies of fear extinction learning and THC challenge in humans; 2) provide evidence that THC facilitates extinction recall in healthy humans; and 2) provides evidence collected by the PI that replicate findings of extinction recall deficits in PTSD patients and support the hypotheses and feasibility of the proposed study.

Impaired Extinction Recall and Dysfunction Activation of vmPFC and HPC during Extinction Recall in PTSD

To assess fear extinction recall in PTSD, Milad and colleagues have developed a fear conditioning-extinction paradigm and has shown less activation in vmPFC and HPC and increased SCRs in PTSD patients (vs. trauma-exposed non-PTSD controls) during extinction recall in response to the a previously extinguished CS+ (CS+E) compared to a non-extinguished CS+ (CS+U)⁷⁰. The PI has collected SCR data as a measure of fear in healthy controls (HCs; n = 15) and PTSD patients (n = 14) in a behavioral pilot study of fear extinction learning and recall using the study design proposed here. Similar to Milad et al.⁷⁰, when recall of extinction was tested 24 hours after extinction learning PTSD patients exhibited recovery of fear, as evidenced by increased SCRs

[figure not shown]

Fig. 2: Deficits in extinction recall in PTSD

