The context-dependent renewal of fear is another factor that can potentially affect the efficacy of exposure therapy. Therefore, the analysis will also test whether THC can induce generalization of extinction across extinction recall (ABB) and renewal (ABA) contexts. We will conduct the same statistical tests on extracted PSC from each ROI, confined to anatomically-based masks, during the Fear Renewal test, as described above for the Extinction Recall test.

We will also look at correlations between BOLD responses in the AMYG, vmPFC, and HPC and the extinction retention index (see below) during Extinction Recall and Fear Renewal tests. In addition, we will implement psychophysiological interaction analyses (PPI)^{40,154,155} to measure task-dependent functional connectivity among the AMYG, vmPFC, and HPC. Separate connectivity analyses will be performed with each group x drug condition (PTSD-THC, PTSD-PBO, HC-THC, and HC-PBO), using vmPFC and HPC as the seed regions followed by between-group connectivity analyses to assess the effect of THC on functional coupling of the vmPFC, AMYG and HPC during Extinction Recall and Fear Renewal.

C.5. Psychophysiology: The primary assessment of fear learning will be a change in SCR, which will be recorded by electrodes attached to the middle phalanges of the second and third digits of the nondominant hand. AcqKnowledge software (BIOPAC Systems) will be used for off-line analysis. We will also obtain subjective US expectancy to the CS+E compared to the CS+U¹⁰³.

C.5.1. Psychophysiological Analysis: SCR for each CS trial will be calculated as described by Milad et al.¹⁰². Extinction recall will be assessed by comparing the mean differential response during the first four trials of the CS+E versus the first four trials of the CS+U. In addition, we will use the “extinction retention index” (ETI) as described by Milad et al.¹⁰² to measure the magnitude of extinction retention. The ETI adjusts the SCR during extinction recall for differences in CR magnitude during acquisition¹⁰⁹. Analyses will be conducted by ANOVA models as above (follow-up t-tests, $\alpha < 0.05$). In addition, we plan to compare and correlate (using Pearson or Spearman rank Correlational analyses) measures of BOLD activation (PSC) and SCR signal to the CS+E vs. CS+U within and across the two contexts/recall and renewal tests.

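### The connectivity (PPI) plan in C.4.1 lists four of the six group-by-drug cells and leaves out both trauma-exposed control (TEC) cells

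*Combined protocol and SAP*

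**What the plan says.** The only connectivity analysis that the protocol specifies is the PPI paragraph in C.4.1. It has two steps. The first is cell by cell: "Separate connectivity analyses will be performed with each group x drug condition (PTSD-THC, PTSD-PBO, HC-THC, and HC-PBO"; the parenthesis closes there. The second is "followed by between-group connectivity analyses to assess the effect of THC on functional coupling of the vmPFC, AMYG and HPC", for Extinction Recall and Fear Renewal. The second step names no groups.

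Connectivity is part of all three specific aims, and each one counts TEC among the controls:

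- Aim 1 covers "connectivity in controls (healthy controls, HC; trauma-exposed non-PTSD controls, TEC". Hypothesis 1C reads: "Relative to PBO, THC will increase functional coupling between the vmPFC and HPC to the CS+E during an extinction recall test in controls".
- Aim 2 is "To compare extinction memory recall success and vmPFC and HPC activation and connectivity between PTSD patients and controls (HC/TEC". Hypothesis 2C reads: "Relative to controls, PTSD patients will show less functional coupling between the vmPFC and HPC to the CS+E during an extinction recall test".
- Hypothesis 3C expects coupling in PTSD patients on THC to be "similar to extent of connectivity observed in controls (HC/TEC".

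**The concern.** The wording before the parenthesis calls for every combination of group and drug. The parenthesis then gives a closed list, with nothing to mark it as an example, and the two missing cells are exactly the TEC cells. An analyst who follows the list leaves TEC out. An analyst who follows the words before it keeps TEC in. Both could say they followed the plan, so the choice could be made after results are seen.

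The comparator matters here. C.2 describes TEC as the control group that is also matched to the patients on trauma exposure, whereas HC are non-exposed. With HC alone, PTSD and trauma exposure vary together, and a coupling difference under 2C or 3C could not be attributed to PTSD. The extinction recall study that the plan builds on (section B) reported "less activation in vmPFC and HPC and increased SCRs in PTSD patients (vs. trauma-exposed non-PTSD controls) during extinction recall", which is a comparison against trauma-exposed controls. Hypothesis 1C would also be tested in only one of the two control groups that Aim 1 names.

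**Working it through.** **Reproducing the plan's own figures**

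- C.2: 3 groups of 50 = 150 enrolled; 5 unusable in each of 6 cells = 30.
- 150 − 30 = 120 usable, which agrees with D.1.
- 120 / 6 = 20 per cell, the top of the 15 to 20 range in C.2 and C.6.

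**Counting cells across the protocol**

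| Place | Groups or cells |
|---|---|
| C.1 | PTSD, TEC, HC; THC or placebo |
| C.2 | 6 experimental groups |
| C.4.1, ROI ANOVA | PTSD, TEC, HC by THC, placebo (by stimulus) |
| C.6 | all six cells by name, both TEC cells included |
| C.4.1, PPI list | four cells, no TEC |

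The design gives 3 × 2 = 6 cells and the PPI list gives 4.

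**Could HC in the list mean all controls?** No. C.1 and C.3.1.4 define HC as non-exposed and TEC as a separate group, and the aims write HC/TEC when both are meant.

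**Does other text bring TEC back in?** No.

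- The between-group PPI step names no groups, and its stated purpose is the effect of THC.
- The C.4.1 sentence that repeats the tests for Fear Renewal concerns extracted percent signal change, not PPI.
- The resting-state scan has no connectivity analysis specified.

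**Size if the list is followed, with equal cells**

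- Participants analysed: 4 × 20 = 80. Omitted: 2 × 20 = 40, and 40/120 = 33%. At 15 per cell: 60 analysed and 30 of 90 omitted, the same share.
- Within-group THC versus placebo contrasts: 2 of 3 remain; TEC is lost.
- Pairwise group comparisons: 1 of 3 remains (PTSD versus HC). PTSD versus TEC and TEC versus HC are lost.
- If the ROI group-by-drug structure is carried over to PPI, the interaction has (2 − 1)(2 − 1) = 1 numerator degree of freedom instead of (3 − 1)(2 − 1) = 2. This shows that a different hypothesis is tested; it is not a loss in itself.

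No power loss is claimed. That would require pooling HC and TEC, which the plan does not state.

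**The case against.** The strongest reply is that this is a slip that the rest of the protocol resolves. The aims, the ROI ANOVA and C.6 all include TEC, and nothing states an intent to exclude it. That is probably how the list arose, and it is why the finding is conditional on the list being followed. It does not settle the matter, because the explicit list is the most specific instruction given for PPI and no PPI text contradicts it by naming TEC.

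A second reply is that the list governs only the cell-wise step and the between-group step excludes nobody. This is correct as to the wording. However, the second step is said to follow from the first, so carrying four cells forward is the natural reading. That step needs its groups stated in any case.

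A third reply is that the reach is narrow, and this stands. The randomised THC versus placebo contrast within PTSD, which bears most directly on the project's primary goal, keeps both of its cells, as does the same contrast within HC. The ROI analyses (recall and renewal) and the SCR analyses keep TEC.

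The precedent also has limits. The study against trauma-exposed controls concerned activation and SCR, not connectivity, and the protocol's own pilot compared PTSD with HC. That comparison is legitimate, but it cannot separate PTSD from trauma exposure.

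Two further gaps are separate and are not caused by the list: the between-group step names no PTSD versus control contrast for 2C against any control group, and similarity to controls in 3C has no criterion.

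**Conclusion.** The concern holds: the sentence is wrong as written. It is certain that the list omits both TEC cells; it is not established that TEC was meant to be excluded. If the list is followed, one third of the usable sample (40 of 120, assuming equal cells of 20) has no PPI analysis. Hypothesis 1C is then untested in TEC, and the only specified tests of 2C and 3C lose the trauma-matched comparator. The effect is confined to PPI, but it reaches one hypothesis in each of the three aims. It should be corrected before the connectivity data are analysed.

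**What to change.** In C.4.1, add TEC-THC and TEC-PBO to the PPI list. State that the between-group PPI step uses the same group (PTSD, TEC, HC) by drug (THC, PBO) structure as the ROI ANOVA, and name PTSD versus TEC and PTSD versus HC as contrasts alongside the THC effect, as Aim 2 and hypothesis 2C require. If leaving TEC out of PPI is intended, say so, give the reason, and limit hypotheses 1C, 2C and 3C to HC.

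The cost is one or two sentences plus subject-level PPI models for TEC scans that are already planned: 40 participants × 2 seeds (vmPFC, HPC) × 2 tests (Extinction Recall, Fear Renewal) = 160 models, assuming 20 per cell and one model per seed and test. No new data collection is needed.

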
After screening, if eligible, the participant will continue with an orientation session to explain the procedures and schedule the sessions. Rules and conditions of participation will be carefully explained. We will query participants about any prior history of claustrophobia or anxiety in small spaces. Each subject will complete a detailed questionnaire regarding the presence of any metal implants or metal objects in their body, and other such contraindications for MRI scanning.

C.3.2. Fear Acquisition (Visit 2): During the Fear Conditioning (Context A) phase, there will be two CS+s that will be paired with the US using partial reinforcement. One of these CS+s will be extinguished during the

subsequent extinction phase (CS+E) whereas the other will not (CS+U). The CS+U serves as a within subject, no-extinction control. A third CS will be presented during conditioning *but* never paired with the US (CS-). Assignment of the slide as CS+E or CS+U (paired with US) and CS- (not paired with US) will be counterbalanced across subjects. The US will be delivered immediately following CS+ offset with no delay between the CS+ offset and the US onset. At the beginning of the session subjects will be told to look carefully at the slides because an unpleasant stimulus (US) may follow the slides. They will also be told that they should learn to predict whether the US will occur or not based on which slide was shown. To assess their predictions, subjects will be required to repeatedly rate their US expectancy using a button box on a scale from 1 to 3 (1 = certain that the US will be presented, 2 = certain that the US will not be presented, and 3 = uncertain whether the US will be presented) and subjects will be asked to repeatedly update their rating to reflect their current US expectancy. At the end of the session all participants will be explicitly told to remember what they had learned; in order to strengthen the retention of the CS-US association for the following days. This visit will be conducted at our research laboratory at the EACPHS building.

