C.4.1. fMRI Analysis: Functional data will be processed and analyzed using conventional methods (GLM, event-related design, random effects) with Statistical Parametric Mapping (SPM8; Wellcome Department of Cognitive Neurology, London; www.fil.ion.ucl.ac.uk/spm)¹⁴⁴⁻¹⁴⁷, previously described in our pharmacological fMRI studies^{91,94,148,149} and extinction recall studies^{102,105}. Analysis will implement 2 complementary approaches⁹⁴: 1) a hypothesis-driven anatomically-focused region of interest (ROI)-based analysis; and 2) exploratory whole-brain voxel-wise analysis. Based on our hypotheses, our two main ROIs are vmPFC and HPC; the AMYG, or at least different sub-regions within AMYG, are involved in fear acquisition^{26,36,150} and extinction²⁵, and thus we identify the AMYG as an ROI *a priori*. These anatomically-defined atlas-based ROIs will be based on anatomical landmarks from human atlases¹⁵¹⁻¹⁵³. In addition, vmPFC and HPC activation reported by Milad et al.⁷⁰ will be used to create a 5 mm radius spherical ROI around peak coordinates to examine data in this study for replication. Extracted BOLD percent signal change (PSC) from each ROI, confined to anatomically-based masks, will be subjected to a repeated measures group (PTSD, TEC, HC) x drug (THC, PBO) x stimulus (CS+E, CS+U) omnibus ANOVA during Extinction Recall. We will test for significant ($p < 0.05$) group x drug x stimulus; all significant main effects and interactions will be followed up by post hoc t-tests with an alpha level of 0.05, two-tailed. If appropriate, we will also include age, gender, and other variables (e.g., mood effects) as additional potential covariates in a separate ANCOVA. For the second approach (whole-brain, voxel-wise), we will employ the same ANOVA approach across the entire brain to search for effects in other areas in an exploratory search to generate hypotheses for subsequent study. Statistical maps for the whole brain analysis will be created using a threshold of $p < 0.001$ with a cluster threshold of 10 voxels. Within the ROIs, a small volume threshold ($p < 0.05$, corrected for multiple comparisons) will be used.

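### The recall and renewal SCR comparisons are not adjusted for pre-drug acquisition SCR; adding it to the THC versus PBO tests is a cheap improvement of uncertain, probably modest, size

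*Combined protocol and SAP*

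**What the plan says.** C.5 makes change in SCR the primary assessment of fear learning. C.5.1 then defines the recall test: "Extinction recall will be assessed by comparing the mean differential response during the first four trials of the CS+E". The comparator is the matching opening set of CS+U trials. The model is given only by reference: "Analyses will be conducted by ANOVA models as above". That points back to the group by drug by stimulus ANOVA of C.4.1, with follow-up t-tests at two-sided 5%.

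Acquisition appears once in C.5.1, through the ETI, which is used in addition to the main comparison: "The ETI adjusts the SCR during extinction recall for differences in CR magnitude during acquisition". The formula for the index is left to a cited study.

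C.4.1, written for the imaging data, has an optional clause: if appropriate, "we will also include age, gender, and other variables (e.g., mood effects) as additional potential covariates in a separate ANCOVA". Acquisition SCR is not named there.

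On design, C.3.2 says of acquisition that "there will be two CS+s that will be paired with the US using partial reinforcement", adds a third cue (CS-) that is never paired, and notes that "The CS+U serves as a within subject, no-extinction control". C.3.3 confirms that psychophysiological responding is recorded during acquisition as well as extinction. C.3.3.1 places the capsule at Visit 3, so acquisition SCR is a pre-drug measure.

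**The concern.** People differ in how strongly they condition. Where that difference carries through to the recall test, it adds to the error variance of the THC versus PBO comparisons in Aims 1 and 3. The trial already collects a pre-drug measure of it on the same response system. The plan regards that measure as relevant, since it builds an index from it, but does not let it reduce the error in the main comparison.

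The cells are small: 15 to 20 usable participants in each of six. The hypotheses for Aims 1 and 3 are also worded as SCR to the CS+E itself, and a follow-up t-test on that cue alone has no CS+U subtraction to help it. At stake is precision. The unadjusted drug comparison is protected from bias by randomisation.

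**Working it through.** **Inputs from the documents.** Two-sided alpha 0.05 (C.4.1). Cohen d 0.8 to 1.5, and 15 to 20 usable per cell (C.6). From C.2, 150 − 30 = 120 usable, and 120 / 6 = 20 per cell.

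**Assumed input.** r, the within-cell correlation between the acquisition covariate and the recall outcome. The documents give none, so a range is shown.

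**The plan's own figure.** C.6 states more than 90% power. For a two-sample t-test with n per arm, the noncentrality is λ = d × √(n/2), with 2n − 2 df.
- n = 20, d = 0.8: λ = 0.8 × √10 = 2.530, 38 df, power 69.3%.
- n = 15, d = 0.8: λ = 0.8 × √7.5 = 2.191, 28 df, power 56.2%.

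For one THC versus PBO contrast within one group, 90% is reached only at d of about 1.05 (n = 20) or 1.23 (n = 15). The stated figure is therefore not reproduced at the low end of the quoted range. That is a separate matter; here it shows only that precision is scarce.

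**With the covariate.** Residual variance is multiplied by 1 − r². Chance imbalance in the covariate multiplies the variance of the contrast by about 1 + 1/(2n − 4), and one df is lost:

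λ = d × √(n/2) / √[(1 − r²)(1 + 1/(2n − 4))], with 2n − 3 df.

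Example, n = 20, r = 0.5: 0.75 × (1 + 1/36) = 0.7708; 0.8 / √0.7708 = 0.911; λ = 0.911 × √10 = 2.881; 37 df; power 80.1%.

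| d = 0.8 | unadjusted | r = 0 | r = 0.2 | r = 0.3 | r = 0.5 | r = 0.7 |
|---|---|---|---|---|---|---|
| n = 20 per arm | 69.3% | 68.1% | 69.9% | 72.2% | 80.1% | 92.5% |
| n = 15 per arm | 56.2% | 54.5% | 56.2% | 58.4% | 66.8% | 82.7% |

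Break-even is at |r| of about 0.17 (n = 20) or 0.20 (n = 15). The largest loss, at r = 0, is 69.3 − 68.1 = 1.2 points or 56.2 − 54.5 = 1.7 points.

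**How large could r be?** As an illustration, let a person effect with variance 1 drive acquisition with loading 1, CS+E recall with loading a, and CS+U recall with loading 1. Each measure has independent noise of variance v (0.5 or 1). Then:
- with the difference score, r = (a − 1) / √{[(a − 1)² + 2v](1 + v)};
- with CS+E alone, r = a / √[(a² + v)(1 + v)].

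| loading a | size of r, difference score | r, CS+E alone |
|---|---|---|
| 1.0 | 0 | 0.50 to 0.67 |
| 0.8 | 0.10 to 0.16 | 0.44 to 0.61 |
| 0.5 | 0.24 to 0.37 | 0.32 to 0.47 |
| 0.3 | 0.31 to 0.47 | 0.20 to 0.32 |

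The difference score removes all of the person effect only if both cues carry it equally. For loadings of 0.5 and above, the covariate helps the CS+E-alone test more; at 0.3 the order reverses. All loadings are assumed.

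**Where there is less to gain.** At d = 1.5, unadjusted power is already 97.7% (n = 15) and 99.6% (n = 20). If HC and TEC are pooled for Aim 1, arms are 30 to 40 and unadjusted power at d = 0.8 is 86.1% to 94.2%.

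**The case against.** The main counter-argument is the design. The outcome is a within-person contrast between two cues that were both paired with the US and counterbalanced, and C.3.4 says the contrast is meant to isolate extinction recall from recall of conditioning. Much stable reactivity is therefore subtracted already. A reader might infer that all variation in conditionability passes into the error term; the documents do not support that. What remains is variation that the two cues carry unequally, which is plausible because only one cue is extinguished, and tests on the CS+E alone.

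Second, r may be low. Acquisition takes place in a testing room in Context A; recall is in the scanner in Context B, with extinction in between. This stands, and it is why the gain is given as a range.

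Third, the plan does not ignore acquisition. The ETI adjusts for it, and the optional ANCOVA clause could admit it. This stands as a limit on the criticism. But a separate index does not sharpen the main comparison, and an optional clause that does not name the variable leaves the choice until after the data are seen.

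A reader might also infer that an index built on acquisition is less efficient than a covariate. The documents do not give the ETI formula, so that cannot be judged. Nor is the adjustment free: below about r = 0.2 it slightly reduces power.

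**Conclusion.** The point holds as an efficiency improvement. C.5.1 leaves a valid pre-drug covariate out of the randomised drug comparisons of recall SCR, and the analysis of renewal inherits the same gap. Nothing here shows bias or invalidity in the unadjusted analysis.

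At d = 0.8 the gain in one within-group contrast is about 2 to 3 points at r = 0.3 and about 11 points at r = 0.5. It is larger only if r is near 0.7, which lies above every value in the illustrative model. The loss is at most 1 to 2 points if r is near zero. The gain shrinks for pooled controls and larger effects, and probably for the CS+E minus CS+U difference compared with the CS+E alone.

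These figures assume a linear relation, a common within-cell correlation and roughly normal residuals. The argument does not carry over to Aim 2: diagnosis is not randomised, and acquisition may itself differ by diagnosis, so adjustment would change the question being asked.

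**What to change.** In C.5.1:

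- Prespecify Visit 2 acquisition SCR as a covariate in the THC versus PBO comparisons of recall and renewal SCR (Aims 1 and 3). In the repeated-measures model, include its interaction with stimulus; a main effect alone leaves the drug by stimulus test unchanged.
- Define it as the mean acquisition response to the CS+ cues minus the CS-. Do not use CS+E minus CS+U at acquisition: both cues are treated alike until extinction, so that score is expected to be near zero and mostly noise.
- State that the ETI is a secondary summary and that the covariate-adjusted comparison is the main one.
- For PTSD versus controls (Aim 2), report results with and without the covariate.

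The cost is one model term, about one degree of freedom per contrast, and a few sentences of text. No new data are needed, since the ETI already requires acquisition SCR. If the pilot data described in section B include acquisition SCR, they could supply an estimate of r before the text is fixed.

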to the CS+E that did not differ from SCR to the CS+U, as compared to HCs, which displayed lower SCRs to the CS+E (Fig. 2).

THC Facilitates Retention of Extinction Memory via Increased Recruitment of the vmPFC and HPC

The PI has previously demonstrated that 7.5 mg oral THC facilitated retention of extinguished fear and prevented spontaneous recovery of fear in healthy humans⁸⁷ (see Fig. 1). Recently, in a separate study, the PI has collected fMRI data investigating the effect of cannabinoids on the underlying neural circuitry involved in the recall of extinction memory in 28 healthy adult volunteers using the study design proposed here. Preliminary fMRI results suggest that THC administration during extinction learning subsequently increases vmPFC activation and functional coupling (psychophysiological interaction; PPI) with the HPC to the CS+E (vs. the CS+U) during recall of extinction memory as compared to PBO⁹⁵ (Fig. 3).

[figure not shown]

Fig. 3: THC increases vmPFC activation and functional HPC-connectivity at extinction recall; [name] et al.⁹⁵

C. Research Design and Methods

C.1. Overall Study Design: In a randomized, double-blind, placebo-controlled, between-subjects design, we will couple a standard Pavlovian fear extinction paradigm in fMRI with an acute pharmacological challenge with oral dronabinol (synthetic THC) or placebo (PBO) 2 hours *prior to extinction learning* in patients with PTSD, trauma-exposed controls without PTSD (TEC), and non-exposed healthy controls (HC) and test extinction memory recall 24 hours after extinction learning. This provides the most translational and critical test to determine if consolidation effects of THC will facilitate subsequent extinction recall in PTSD patients.

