C.6. Power Analysis: We have conducted several power calculations in our previously published work, used to determine the sample sizes proposed here. First we have consistently found that an n of 14-16 HCs and an n of 14-16 PTSD patients provide adequate power to observe: 1) vmPFC and HPC signal differences between groups during extinction recall; and 2) THC’s effects on AMYG and vmPFC activation and functional connectivity in HCs. Given that the effect sizes tested within- and between-groups in previous studies have ranged between moderate – large (Cohen d 0.8-1.5). With the anticipated cohort 15-20 subjects per group (PTSD-THC, PTSD-PBO, TEC-THC, TEC-PBO, HC-THC, HC-PBO), who complete the entire protocol with usable fMRI and SCR data, this number will confer >90% power to detect moderate effect sizes expected from our significance testing.

D. Additional Human Subjects Information

D.1. Probable Duration of the Study: The study is intended to run for 4 years. During this time we expect to collect data from 120 usable subjects.

D.1.1. Proposed Involvement Per Participant: The total time commitment estimated per participant is 11 hours across all study visits. This is broken down below:

Visit 1: Screening and Study Entry: Approximately 3 hours

Visit 2: Fear Acquisition: Approximately 1 hour

Visit 3: Fear Extinction: Approximately 5 hours

Visit 4: Fear Extinction Recall, Fear Renewal Test, and Debriefing: Approximately 2 hours

D.2. Location Where Research is to be Conducted: The informed consent, diagnostic tests, and the fear acquisition behavioral session will be conducted in the research offices located at the EACPHS building. Functional imaging and the extinction learning, extinction recall/fear renewal, and debriefing session will be conducted at the WSU Magnetic Resonance Research Facility (MRRF), located in the basement of Harper University Hospital.

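### C.6 claims more than 90% power for moderate effects without tying it to a contrast; for THC vs placebo within PTSD, power at d = 0.8 is 69% with 20 per cell and 56% with 15

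*Combined protocol and SAP*

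**What the plan says.** C.6 (Power Analysis) reports that "the effect sizes tested within- and between-groups in previous studies have ranged between moderate – large (Cohen d 0.8-1.5". It then continues: "With the anticipated cohort 15-20 subjects per group (PTSD-THC, PTSD-PBO, TEC-THC, TEC-PBO, HC-THC, HC-PBO", and concludes that, given complete and usable data, "this number will confer >90% power to detect moderate effect sizes expected from our significance testing". It attaches no contrast, outcome, alpha or effect scale to that figure.

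Section D.1 sets the expected yield: "During this time we expect to collect data from 120 usable subjects". Over six cells that is 20 each. Section C.2 has already taken out about 30 of 150 participants (5 per cell) as unusable.

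The design in C.1 is described as "In a randomized, double-blind, placebo-controlled, between-subjects design". Section A says that "the primary goal of the proposed project is to test the hypotheses that administration of an exogenous CB1 agonist" will restore extinction recall in PTSD patients. Hypothesis 3A puts it as: "Relative to PBO, THC will decrease SCRs and US expectancy ratings to the CS+E during an extinction recall test in PTSD patients". Hypotheses 3B and 3C make the matching predictions for activation and connectivity.

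C.4.1 specifies a group x drug x stimulus ANOVA followed by two-tailed t-tests at 0.05, and C.5.1 uses the same approach for skin conductance.

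**The concern.** One unqualified power figure covers tests that use very different numbers of subjects. The THC effect within PTSD uses only two of the six cells, 30 to 40 people, and it is the comparison that the plan calls its primary goal. A reader of C.6 would put the chance of missing a moderate effect there below 10%. If it is really 31% to 44%, both the judgement that the sample is sufficient and the reading of a null Aim 3 result change.

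**Working it through.** **Inputs.** Cell size n = 20 (120 / 6, D.1) or 15 (the floor in C.6 and C.2). Effect d = 0.8, the low end of the C.6 range. Alpha 0.05 two-tailed (C.4.1). Drug between subjects (C.1), with half of participants on dronabinol (C.3.3.1). No further attrition is taken off, because these are usable subjects.

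**Formula.** For two independent groups, df = n1 + n2 − 2, δ = d·√[n1·n2/(n1 + n2)], and power = P(|T| > t(0.975, df)), where T is noncentral t with parameter δ. The effect size d is on whatever outcome is compared between the cells.

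**THC vs placebo within PTSD, d = 0.8.**
- n = 20: δ = 0.8·√10 = 2.530, df = 38, critical t = 2.024, power 69.3%.
- n = 15: δ = 0.8·√7.5 = 2.191, df = 28, critical t = 2.048, power 56.2%.

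The stated figure is therefore not reproduced for this contrast. The chance of a miss is 31% and 44%.

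**Across the plan's range, same contrast.**

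| d | 20 per cell | 15 per cell |
|---|---|---|
| 0.8 | 69% | 56% |
| 1.0 | 87% | 75% |
| 1.15 (midpoint) | 94% | 86% |
| 1.5 | >99% | 98% |

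Solving for 90% power gives d = 1.05 (20 per cell) and d = 1.23 (15 per cell).

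**More favourable choices at d = 0.8 (20 / 15 per cell).** One-sided t: 79.9% / 68.9%. Error df pooled over six cells (6n − 6): 70.8% / 58.2%. Neither reaches 90%.

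**Effect scale.** Hypothesis 3A is worded on CS+E, while C.5.1 assesses recall as CS+E against CS+U. Suppose d = 0.8 is a raw CS+E effect, THC does not affect CS+U, the two stimuli have equal variance, and the test is on the difference. The effect then becomes 0.8/√[2(1 − ρ)], where ρ is the correlation between stimuli. At ρ = 0.5 this is again 0.8, and power is unchanged. Setting it equal to 1.052 or 1.226 gives ρ = 1 − 0.5·(0.8/1.052)² = 0.71 for 20 per cell, and ρ = 1 − 0.5·(0.8/1.226)² = 0.79 for 15. The plan gives no value for ρ.

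**Other contrasts at d = 0.8.**

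| Contrast | 20 per cell | 15 per cell | Assumption |
|---|---|---|---|
| Drug, all groups (60 v 60; 45 v 45) | 99% | 96% | drug effect equal across groups |
| Drug, pooled controls (40 v 40; 30 v 30) | 94% | 86% | drug effect equal in HC and TEC |
| Paired CS+E vs CS+U in one cell, δ = d·√n, df = n − 1 | 92% | 82% | d is on the paired difference |
| PTSD vs controls, placebo only (20 v 40; 15 v 30) | 82% | 70% | – |
| PTSD vs controls, both arms (40 v 80; 30 v 60) | 98% | 94% | THC leaves the gap unchanged |
| Same, if THC fully closes the gap (d = 0.4) | 54% | 42% | (0.8 + 0)/2 = 0.4 |

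The last two rows matter because Hypothesis 3A predicts that THC brings patients to levels like those of controls.

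**The case against.** The strongest reply is that C.6 never attaches its figure to THC vs placebo in PTSD. It speaks of significance testing in general, and several tests in the plan do exceed 90% at d = 0.8. That stands, and it limits the finding. A reader might infer that the figure is wrong throughout, or that the trial as a whole is underpowered. The documents support neither, since pooled drug comparisons and, with 20 per cell, the paired within-cell comparison reach it. But a general figure also covers Hypotheses 3A-3C, and there it is not delivered at d = 0.8.

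A reader might also infer that the plan names no test anywhere. It does, in C.4.1 and C.5.1. What is missing is the link from the power figure to a contrast.

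C.6 gives no cut-point for moderate, so d = 0.8 is an interpretation. At the midpoint of 1.15 with 20 per cell, power is 94% and meets the claim; with 15 it is 86% and does not. This stands as a qualification. A conventional moderate d of 0.5 (an assumption) would be less favourable still: 34% and 26%.

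A difference score could raise power above 90%, but only at a stimulus correlation that the plan does not state.

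Finally, C.6 cites earlier work in which 14-16 per group was adequate. That work concerned differences between patients and healthy controls and THC effects in healthy controls. Section A says that direct tests in PTSD patients had not been done.

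**Conclusion.** The concern holds for the contrast that carries the primary goal. With moderate read as d = 0.8, and d on the outcome compared between cells, THC vs placebo within PTSD has 69% power (20 per cell) or 56% (15 per cell), not more than 90%. The stated power is reached only from d of about 1.05 or 1.23, toward the upper part of the plan's range.

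These figures assume a two-tailed t-test at 0.05 and no multiplicity adjustment; adjusting over regions or outcomes would lower them. A reader might infer that the sample must grow. That does not follow, because the plan does not establish that the true effect in PTSD is as small as 0.8. The defect is a power statement broader than its support.

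**What to change.** Restate C.6 by contrast, giving for each the test, alpha, effect scale and assumption.

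- **THC vs placebo in PTSD:** report 69% / 56% at d = 0.8 (20 / 15 per cell) and detectable d at 90% power of 1.05 / 1.23. If the test is on the CS+E minus CS+U difference, say whether d is on that difference; if not, state the assumed stimulus correlation.
- **Keep more than 90% only where it is reached:** drug over all groups if the effect is equal across them (99% / 96%); drug in pooled controls at 20 per cell (94%; 86% at 15); paired CS+E vs CS+U within a cell at 20 per cell (92%; 82% at 15).
- **PTSD vs controls (Aim 2):** report the placebo-only figures, 82% / 70%. Give 98% / 94% for both arms combined only with the condition that THC leaves the gap unchanged, and note that full closure would give about 54% / 42%.

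The cost is one rewritten paragraph and a less favourable stated power for Aim 3. Enrolment, conduct and analysis stay as they are.
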